*FSI group activities in each domain will be supervised closely with verbal, visual, and tactile cues to promote optimal posture and movement quality. **Progression of activities in the PST and FT domains** will be based on therapist assessment of movement quality, specifically the absence form fatigue, and the ability to maintain a level pelvis with hip muscle activation during the task. Therapists will **progress strengthening exercises** when patients are able to demonstrate proper form during the prescribed 8 repetitions (e.g. 80% of 1 repetition maximum). Therapists will be encouraged to push patients to work at a high level of difficulty and progress toward Phase 3 as quickly as possible.

** CON group activities are progressed based on the post-operative timeline indicated above (by phase and week)

A1.3.1. Performance-based Physical Function Measures

Performance-based measures of physical function with well-established reliability and validity will include the 6-minute walk test (**6MW**) (**primary outcome**), 4 meter walk test (4MW), 30 second sit-to-stand test, and the Functional Gait Assessment (FGA) (Table 2). Patients will also perform a 6MW test⁷⁶, which assesses how far a patient walks in 6 minutes. The 6MW test was chosen as the primary outcome because it captures performance over a period of time that best mimics community ambulation with activities of daily living. The 6MW test is reliable and valid in the post-THA population and can detect small changes in function after THA.⁷⁷ The 4MW test measures the time to walk 4 meters and has been used to generate gait speed values, which have been associated with morbidity and mortality in older adults.⁷⁸ Participants will perform the 4MW with instructions to walk in their “normal, everyday pace.” The 30 second sit-to-stand test assesses functional lower extremity strength and endurance, and has been validated and found reliable in older adults at various physical activity levels and physical independence levels.⁷⁹⁻⁸¹ Participants will also perform the FGA, which is a 10-item objective outcome measure designed to measure dynamic balance while walking in the presence of external demands, and will provide information on patients’ stability before and after THA.⁸² The FGA has been shown to be a reliable and valid measure, effective in classifying fall risk in older adults and predicting unexplained falls.^{82,83}

A1.3.2. Self-reported Outcomes

Patients will complete the Veterans RAND 12-item health survey (VR-12), the Western Ontario and McMaster Universities Osteoarthritis Index (WOMAC), and a motivation scale at each visit. The Patient Activation Measure (PAM) survey will be administered only at the baseline visit. The VR-12 is a reliable, self-report survey for assessing health-related quality of life.⁸⁴⁻⁸⁶ The WOMAC assesses the impact of osteoarthritis on pain, stiffness, and disability.⁸⁷ The WOMAC has been shown to be a valid, reliable, and responsive instrument often used in clinical trials.⁸⁷ The PAM survey assesses patient knowledge, skill, and confidence for self-management, as self-efficacy exhibits a positive relationship with preventive actions and health outcomes.^{88,89} The motivation scales asks the participant “How motivated do you feel to participate in physical therapy?”, and rating on a 0 (not at all motivated) to 10 (very motivated) scale.

A1.3.3. Muscle Performance Measures

Isometric strength of the quadriceps and hip abductor muscles will be assessed on a handheld dynamometer. All strength testing will be performed in positions that minimize the risk of hip dislocation post-operatively, while still allowing for optimal trunk and pelvic stabilization. Isometric quadriceps strength testing will be performed in sitting at 0° hip flexion and 60° knee flexion. Isometric hip abduction strength testing will be performed in side lying at 0° flexion/extension and 0° hip abduction.³³ Testing will include warm-up repetitions, followed by three separate maximal voluntary isometric contractions while receiving visual and verbal feedback. Additionally, patients will complete hip abductor endurance testing using a static single-limb balance test, based off of the Trendelenburg test proposed by Hardcastle¹⁴ and measurement of pelvis angle by Youdas, *et al.*⁹⁰ and Asayma *et al.*⁹¹ This modified Trendelenburg test¹⁴ assesses neuromuscular control during timed, single limb stance and indicates the ability of the lateral hip muscles to maintain pelvic control during closed-chain, functional tasks and therefore serves as a measure of hip abductor muscle endurance.¹⁴ This test will be performed in the GRECC Human Movement Analysis Lab using a high-speed motion-capture system to assess lateral pelvic tilt (see D2.3.1). Differences will be analyzed in pelvic tilt angles from preoperative to postoperative assessments during the single-limb task on the surgical leg.

A1.3.4. ActiGraph Physical Activity Monitoring

ActiGraph physical activity monitors (ActiGraph Inc. Pensacola FL) will be used to obtain an objective measure of physical activity (PA). ActiGraph activity monitors assess PA using accelerometry, which allows objective evaluation of the relative volume (steps/day) and intensity (activity counts) of physical activity with high validity and reliability.⁹²⁻⁹⁴ Each participant will wear the ActiGraph for at least 4 days at all time points to assess average daily PA (steps/day).^{95,96} The ActiGraph monitor will be used only for outcome data (not intervention) and provides no feedback to participants.

Outcome Measures	Baseline	POST ₁	POST ₂	POST ₃
Physical Function: 6MW	X	X	X*	X
Physical Function 4MW, 30 sec Sit-to-Stand, FGA	X	X	X	X
Muscle Strength: Quadriceps and Hip abductor strength, Trendelenburg	X	X	X	X
Peak internal hip abduction moment	X	X	X	X
ActiGraph Physical Activity Monitors	X	X	X	X
Self-report: VR-12, WOMAC, PAM survey (baseline only), Motivation scale (POST ₁ and POST ₂ only)	X	X	X	X
Safety Outcomes: Falls, injury, pain		X	X	X

*Primary end-point and outcome measure

Table 2 Timetable of Outcome Measures

A1.3.5. Biomechanical Analysis and Measures of Pelvic Stability

Lower extremity biomechanical measures will be used to quantify movement patterns during level walking and stepping up/down from an 8" stair step in the GRECC Human Movement Analysis Lab. Similar protocols for the assessment of movement patterns have been performed in the pilot studies leading to the current proposal and other previous work on movement patterns for patients with hip OA and THA.^{24,45,51,52} Surgical limb peak internal hip abduction moment, will be calculated with 3-D instrumented motion analysis. Briefly, lower extremity joint kinematics will be quantified from wearable sensors and retro-reflective markers tracked via an 8-camera, high speed motion capture system (Vicon Motion Systems, Oxford, UK) at 100 Hz. Lower extremity joint kinetics will be derived from ground reaction force data recorded from two force platforms (2000 Hz) embedded in the floor that are synchronized with the cameras (Bertec, Columbus, OH). Continuous internal hip abduction moments will be calculated during functional task performance using a standard inverse dynamics approach integrating kinematic and kinetic data using Visual 3D software (C-Motion, Germantown, MD). From the continuous hip moments, peak surgical limb internal hip abduction moments during the Loading Response phase of the stance period of the walking trials will be collected. All joint moments will be normalized to participant body mass. [name] (co-investigator) will oversee all aspects of the biomechanical analysis.

A1.3.6. Safety Outcomes

Patients will report falls, musculoskeletal injury history, and pain levels at rest and with activity (numerical pain rating scale [NPRS; 0= no pain, 10= worst possible pain]) on a weekly basis during the intervention and biweekly via phone calls through 26 weeks. Additionally, treating physical therapists will monitor incidence of musculoskeletal injury (specifically, hip dislocation) by completing a brief examination at each treatment session. Finally, surgical success will be evaluated by incidence of neurologic palsy, infection, deep vein thrombosis/pulmonary embolism, skin necrosis, delayed wound healing, vascular injury, and surgical revision.

A1.4. Procedural Reliability

Procedural reliability is critical to the success of the proposed intervention. We have established mechanisms to assure consistency of treatments across sites consistent with previous reports of procedural oversight and treatment fidelity.⁹⁷ Participating Veterans will attend outpatient PT visits at one of the following locations- Denver VAMC (9th Ave. clinic), AMC PT program clinic, PFC Floyd K. Lindstrom Outpatient Clinic at Colorado Springs, or Golden Outpatient Clinic with structured oversight seen to by the investigative team. [name], PT, PhD (co-investigator) will oversee the standardization and implementation of the rehabilitation programs at the clinical site. The PI will oversee the methodological issues related to fidelity of treatment across treating therapists and address any clinical trials issues specific to rehabilitation. She will meet regularly with [name] to troubleshoot any difficulties that arise and provide additional oversight to ensure the fidelity of the investigation.

There will be 2 therapists to treat study patients (1 FSI and 1 CON) at each PT clinic. This will minimize the potential for contamination, as each therapist will be unfamiliar with the specifics in the other program. Furthermore, patients by group will be scheduled for morning vs. afternoon treatments to minimize patient contamination. [name] and the PI will provide 3 initial training sessions to review treatment protocols and documentation. FSI-trained therapists will receive instruction on providing visual, verbal, and tactile feedback during FSI activities, as well as instructions on monitoring pelvic position to maximize muscle recruitment and movement quality and how to determine form fatigue. This specific training will ensure successful implementation of the FSI program and ensure therapists are providing the same feedback to patients during exercise and using the same criteria to dose exercise. CON-trained therapists will receive instruction on topics to be included for patient education, specific activities to include in the clinic and home exercise programs, and proper dosages for each activity. A manual will be provided to the clinic with protocol details for each group (FSI and CON), clinic and home exercises, and documentation forms. Separate manuals for each program will be produced, and therapists will be instructed not to share intervention details with other therapists. In addition, every month for the first year, and every 3 months thereafter, treating therapists from the clinical site will meet with [name] to discuss treatment guidelines and any issues that have surfaced. [name] will monitor patient treatments weekly for the first 2 patients in each treatment group. Should new therapists be added to the treatment team during the course of the proposed investigation, the same procedures for initial training/monitoring will be implemented. For each clinical site, a procedural reliability checklist (Appendix) for adherence to the rehabilitation protocol across therapists will be completed weekly for each of the first 2 patients in each treatment group. For the remaining patients, procedural reliability will be evaluated at the midpoint and end of treatment. If the procedural reliability is below 90%, additional training sessions will be scheduled with individual therapists. Procedural reliability using this approach for our existing studies with patients following knee and hip arthroplasty (n=192 patients) at similar clinical sites has been 96.6%. Therefore, based on our extensive experience with this approach with procedural reliability in similar trials (NIH R01-HD065900, R03-AR054538, K23-AG029978), we expect the procedural reliability to be greater than 90% for all observations.

A1.5. Data Management

Study data will be collected and managed using the REDCap (Research Electronic Data Capture) platform. REDCap is a secure, web-based application designed to support electronic data capture for research studies, providing user-friendly case report forms, real-time data entry validation (e.g. for data types and range checks), audit trails, transaction logs, and a de-identified data export mechanism to common statistical packages. Data will be placed on the REDCap Instance at the Colorado Clinical and Translational Sciences Institute (CCTSI). This data will be used solely for the purposes defined for this specific study. Data placed on the CCTSI REDCap Instance will not be accessed or used for any other study or purpose, and will only be accessed by VA-credentialed personnel. The CCTSI REDCap Instance is a highly secure, nationally-utilized data management system, and it is housed within the highly-secure environment at the University of Colorado.

A1.6. Data Analysis

The primary outcome for this study is change in 6MW distance from baseline to POST2 (end of study intervention). Secondary physical function and muscle performance outcome measures include change in 4MW, 30 sec sit-to-stand, isometric hip abductor strength, and hip abductor muscle endurance. Secondary self-report outcome measures include the WOMAC and VR-12. Measures of movement compensation after unilateral THA include *peak internal hip abduction moments* during **walking from baseline to POST2**. Preliminary descriptive and graphical analyses (e.g. boxplots, scatterplots, and profile plots over time) will be used for data checking and visualization. All analyses will assume a two-sided test of hypothesis, with a significance level of 0.05, and be performed in SAS v9.4 or higher and R v3.2.2 or higher.

Primary Analysis: The primary analysis will be an intent-to-treat comparison between groups of the change in 6MW distance from baseline to POST2 (end of intervention). Statistical inference regarding the difference between treatment groups will be based on the estimated coefficient for a group indicator variable in an analysis of covariance (ANCOVA) model with the change from baseline at POST2 for the 6MW distance being the response variable. Additional covariates will include the stratification variables (surgical approach and Veteran/non Veteran) and the baseline value of the 6MW distance to improve the precision of the estimate.

The conclusion about differences between treatment groups will be determined by this single statistical test to protect against an elevated risk of false positive conclusions. A similar analysis will be performed on the change from baseline to POST3 to determine persistence of group differences to 26 weeks. Additionally, a sensitivity analysis will be performed utilizing a mixed-effects model and all available data, with estimation of the change from baseline to POST2 and POST3. If the sensitivity analysis is not consistent with the primary analysis, the results will be considered inconclusive.

Secondary Analyses: Differences between groups in the secondary outcomes for physical function, muscle strength and endurance, and peak internal hip abduction moment, from baseline to POST2 will also be analyzed as described above. All outcomes will be analyzed at POST3 to evaluate the long-term impact and sustainability of the FSI training. We anticipate that secondary outcomes will be correlated with the primary outcome, so that similar effects on secondary outcomes will reinforce significant differences in the primary outcome. Failure to observe consistency between primary and secondary outcomes will be taken as evidence that the effects of FSI intervention are not clear, and that further study is necessary to resolve inconsistencies. This approach reduces the risk of false-positive conclusions resulting from multiple statistical tests.

A1.7. Sample Size Estimates

Statistical power was estimated using variability estimates from Heiberg *et al.* (2015), where the change in 6MW distance was assessed for 60 participants following THA.⁹⁸ Because Heiberg's target population was comparable to that currently proposed, and their sample size was 3 times that of our pilot study, our estimates using these data⁹⁸ are expected to serve as the best estimate of samples size. As such, the observed SD at 3 months post-surgery for the sample was 81.3. Based on this SD, a 2-sample, 2-sided t-test at the 5% level with 80 patients (40 per group) would have 90% power to detect a clinically meaningful difference of at least 59.7 meters.⁹⁹ The primary analysis using linear regression will be conditioned on the baseline value of each outcome measure, in addition to the sex and surgical approach stratification variables, thus improving the precision of (and giving greater power to) the estimates. We will recruit 150 participants (75/group) to allow for loss to follow-up.

A1.8. Alternative Approaches and Limitations

Missing Data. All participants with outcome measurements will be included in the intent-to-treat analysis. Although we will encourage participants to be fully compliant to their assigned treatment regimen and testing sessions, they will not be dropped from follow-up measurements for lack of compliance. The importance of complete follow-up will be stressed during enrollment and consent, and repeated during study participation. Participants will be contacted repeatedly if they miss follow-up visits, and all efforts will be made to get participants to return for scheduled follow-up visits. Although statistical methods can be used to "adjust" for missing data, these methods rely on the untestable assumption that data are "missing at random" so that the effect of the missingness can be removed through statistical modeling. We will instead focus on preventing missed follow-up visits.

Differences in surgical approach. There remains a paucity of prospective data comparing physical function outcomes with posterolateral versus direct anterior THA surgical approaches. Therefore, including both surgical approaches (and stratifying by approach) will increase the generalizability of the study. Furthermore, this strategy may also provide additional insights regarding any potential differences in surgical approaches. Finally, we have intentionally chosen not to include less common, alternative THA surgical approaches (e.g. direct lateral) to focus stratification on the most commonly used THA surgical approaches.

A1.9. Timeline

Anticipated project timeline and cumulative enrollment. Local IRB approvals will be finalized prior to initiating the investigation. Study enrollment will start in months 3-4 and continue through the first part of year 4, with a targeted accrual rate of 2-3 patients/month. Abstract and manuscript preparation will begin in years 2-3, but will increase in year 4.

A1.10. Future Investigation

1) Evaluate strategies for dissemination and implementation of study findings in clinical practice.

While the proposed FSI intervention is novel, it has been designed for practical implementation in clinical settings to facilitate more rapid dissemination of study findings into routine clinical practice. We will explore strategies to optimize such dissemination and implementation.

2) Determine the optimal length of FSI intervention.

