One hundred-fifty patients aged 50-85 years with hip OA, scheduled for a unilateral, primary THA will be enrolled, with at least 80 patients expected to complete the study. Patients will have a THA performed by surgeons who will refer patients who meet the following criteria: 1) no severe contralateral leg OA (< 5/10 pain with stair climbing) nor other unstable orthopaedic conditions that limit function, 2) no neurological or pulmonary problems that severely limit function, 3) no uncontrolled hypertension or diabetes, and 4) body mass index ≤ 40 kg/m² (for motion capture reliability). Referring surgeons will perform THA using their preferred surgical approach (anterior or posterolateral). Upon referral and prior to surgery (PRE), eligible patients will visit the **GRECC Human Movement Analysis Lab** for informed consent and baseline

measurements. Two weeks after surgery, with physician approval, they will be **randomization into 1 of 2 treatment arms: FSI (experimental) group or CON (control) group**. The randomization process and maintenance of treatment code records will be managed by [name] (biostatistician), who will not be involved in patient testing/treatment. This will maintain the double-blinded condition for participants/researchers collecting data.

A1.2. Rehabilitation

Following THA surgery, standardized **inpatient** rehabilitation programs will be implemented for all patients (Figure 4). Upon returning home, patients in both groups will receive a phone call and/or home visits (if necessary) from a study physical therapist from our research team to ensure safety, provide ADL training, and monitor for complications. Randomization and initiation of study treatment will follow this 2-week recovery period to allow for early recovery before intervention. Following randomization, both groups will participate in an 8-week outpatient rehabilitation program (~40 minutes per session) at the outpatient PT Clinic, or at the

[figure not shown]

Figure 2. Peak internal hip abduction moment changes over time for the pilot-study intervention and control groups for the surgical limb during walking, step-up, and step-down tasks. (n=5 Control; n=10 Intervention)

[figure not shown]

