The **FSI program** will target the integration of strength gains into lumbopelvic stability and movement quality during daily living, thus optimizing physical function for Veterans after THA. The exercise program consists of rehabilitation techniques to address the well-established, long-term impairments of muscle weakness and functional movement compensations after THA.^{11,30,39} Specifically, the FSI intervention involves strengthening for the hip musculature similar to previously published protocols^{22,56}, combined with focused techniques emphasizing early initiation of hip muscle recruitment to stabilize the pelvis, thus integrating strength and movement pattern training to maximize functional recovery. The FSI program includes therapeutic exercise in 3 domains: **pelvic stability (PST) training, functional training (FT), and strength training (ST)** (Table 1). Activities in the **PST** domain include early surgical-limb weight bearing activities and core muscle strengthening exercises designed to progressively increase in difficulty based on patient performance benchmarks and therapist monitoring. Activities in the **FT** domain focus on gait and stair climb exercise, which progresses to higher level agility training. The **ST** domain includes progressive, resistance exercise to remediate strength in the lower extremities in the major muscle groups impacted by THA.³³ The ST exercises will include use of weighted pulleys and weight-training machines. Therapists will determine an 8-repetition maximum for each muscle group and weight will be increased by at least 10% every 2 weeks to maximize muscle hypertrophy and strength gains. The novelty of the FSI program lies in the focus on **integrating strength and function** through progressive functional exercises promoting muscle coordination around the hip, thus optimizing alignment between femur, pelvis and lumbar segments.¹³

Control Group Rehabilitation Program

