There is no standard of care for rehabilitation following THA.⁵³ Observed practice patterns from previous investigations³³ and discussion with physical therapists indicate that patients receive rehabilitation services during the 2-3 day hospital stay after THA, but not routinely after hospital discharge. Yet, to control for attention and volume of rehabilitation for the FSI group, patients in the control group will attend outpatient physical therapy for 14 visits (40 minute sessions) over 8 weeks. This control program will mimic the typical postoperative experience for patients in our community, in which patients independently manage their activity. This program will focus on patient education, functional ADL training, and therapeutic exercise. However, the activities in the exercise domain will be limited to low load exercise such as isometric muscle exercise, ROM, and flexibility activities. These activities are specifically designed to mirror usual care activity. These activities will not include progressive strength training exercise or specific functional activity to improve pelvic stability and core muscle strength, which are exclusive to the FSI group.

A1.3. Data Collection and Outcome Measures

Baseline testing will occur 2 weeks prior to THA. To develop a more precise estimate of the trajectory of recovery after THA, we will assess outcomes at 3 times postoperatively. Postoperative testing will occur at intervention mid-point, 4 weeks (POST1); intervention end-point, 8 weeks (POST2) (primary endpoint); and late recovery, 26 weeks (POST3). The 4-week test will allow for identifying if any changes occur early in the intervention, the 8-week test will serve as the primary endpoint for assessing intervention efficacy, and the 26-week test is important to assess persistence of intervention effects. Testing will be performed using standardized procedures described below. Testing may occur remotely via Zoom or video call, at the participant's home, or on the Anschutz campus.

Phase	Functional Strength Integration Program (FSI) *	Control Group Program (CON)**

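### The protocol claims double-blinding that includes participants, but the mechanism it gives can conceal allocation and help blind assessors, not blind participants to the content of clearly different programs

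*Combined protocol and SAP*

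**What the plan says.** Research Methods A1.1 (Patients) places randomization and the treatment codes with a biostatistician "who will not be involved in patient testing/treatment". It then draws the inference: "This will maintain the double-blinded condition for participants/researchers collecting data". No other blinding procedure is described for participants or for assessors.

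The two programs are set out in A1.2, the two program descriptions and the phase table. For FSI, "The ST exercises will include use of weighted pulleys and weight-training machines", loads are set from an 8-repetition maximum, and later phases add foam, balance-board, BOSU and agility work. A note to the table adds: "Therapists will be encouraged to push patients to work at a high level of difficulty and progress toward Phase 3 as quickly as possible". For CON, exercise is "limited to low load exercise such as isometric muscle exercise, ROM, and flexibility activities", alongside education and ADL training. Of the CON activities the plan says "These activities will not include progressive strength training exercise or specific functional activity", the latter meaning activity aimed at pelvic stability and core strength, which is reserved for FSI.

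A1.6 lists WOMAC and VR-12 as secondary self-report outcomes. Under Secondary Analyses it says that "similar effects on secondary outcomes will reinforce significant differences in the primary outcome", and that a lack of consistency would leave the effect of FSI unclear.

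**The concern.** A blinding statement tells the reader which biases the design has dealt with. Here the statement covers participants, but the step offered in support acts only on the people who might see the codes. If it stands, the trial can be reported as double-blind when participants know from the first session what kind of exercise they have been given.

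This bears on how the results are read. A participant who is pushed hard on machines may expect to do well, and one given range-of-motion work may not. Such expectation can move a questionnaire score directly, and can move effort on a walking, sit-to-stand or maximal strength test to a lesser degree. The consistency reasoning in A1.6 treats agreement among correlated outcomes as strengthening the primary result. If several of them share an expectation component, part of that agreement could come from the shared component.

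**Working it through.** The blinding claim contains no figure to recompute, so the check sets the relevant sections side by side. Arithmetic is used only where it helps.

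1. **What the mechanism can do (A1.1).** An uninvolved code-holder can conceal the allocation sequence and help keep data collectors unaware of the arm. Nothing in that step touches what a participant experiences.

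2. **What participants experience (A1.2, program descriptions, phase table).** Visits are twice weekly for 6 weeks, then weekly for 2: 6 × 2 + 2 × 1 = 14. This matches the 14 visits stated for CON, so volume is equal. Content is not. One arm does loaded, progressive, balance and agility work; the other does low-load work with those elements excluded.

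3. **Who else knows (A1.4, Procedural Reliability).** Each clinic has one therapist per arm, trained on that arm's program. Treating therapists therefore cannot be blind.

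4. **Whether participants are masked to the hypothesis.** Three features are compatible with such masking: equal attention, separate therapists and manuals, and morning versus afternoon scheduling by group. The reasons the plan gives are attention and volume for the first (Control Group Rehabilitation Program) and contamination for the separation (A1.4). No text says that participants are told the programs are equivalent, that the hypothesis is withheld from them, or that the success of blinding is checked.

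5. **Which outcomes are exposed (A1.6).** The secondary outcomes named are 4-meter walk, sit-to-stand, hip abductor strength, hip abductor endurance, WOMAC, VR-12 and peak hip abduction moment, which makes 7. Two are self-reported (2/7). The performance and strength tests, like the primary 6-minute walk, depend on effort.

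6. **What does not change (A1.7).** Inputs: difference 59.7 m, SD 81.3 (taken as metres), 40 per group, two-sided 5%. Standardised difference d = 59.7/81.3 = 0.734; noncentrality d × √(40/2) = 0.734 × 4.472 = 3.28; exact two-sample t power 90.03%. The stated 90% reproduces, and blinding does not enter it.

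7. **Illustration only.** The documents give no size for an expectation effect. Assume no true effect and a shift of 0.1, 0.2 or 0.3 SD on one self-report scale, with 40 per group and the same t-test. The noncentrality is 0.447, 0.894 or 1.342, and the chance of a significant difference on that scale is 7.3%, 14.3% or 26.3%, against 5% with no shift. These are rates for one scale tested alone, under assumed shifts.

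**The case against.** The strongest reply is that participants in an exercise trial always know which exercises they do, and that the useful question is whether they know which program is under test. Both arms receive active, supervised programs matched for visits and session length, and both have home exercises. Therapists do not share details, and the groups attend at different times of day. A participant might well not know that theirs is the control program. What participants are told would normally appear in the consent material, which is not in the text available here.

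This reply stands in part. A reader might infer that the trial is open-label, or that only assessors could be blind. The documents do not support that: masking to the hypothesis can be neither confirmed nor excluded. But the reply does not rescue the sentence in A1.1, which rests participant blinding on custody of the codes.

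A second reply is that little depends on it. A1.6 lets a single test on 6-minute walk change decide the conclusion. Secondary outcomes can only reinforce that result or count against it, so biased questionnaires alone cannot make the trial positive. This also stands. It is why the percentages in the illustration must not be read as the trial's false-positive rate.

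A reader might also want WOMAC and VR-12 removed from the consistency reasoning. That would be a debatable trade-off, and inconsistent if effort-dependent tests stayed in. Even their place there is arguable: the Secondary Analyses paragraph does not name self-report separately, although Aim 1 counts both questionnaires as physical function. Pain and falls are safety outcomes and lie outside that reasoning. Dislocation checks by treating therapists are a side issue, since patients also report injuries themselves.

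**Conclusion.** The point holds in limited form. The stated mechanism does not deliver participant blinding to program content, treating therapists are not blind, and the available text describes no masking of participants to the hypothesis. Assessor blinding is claimed and is compatible with the mechanism.

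The effect is on interpretation. Two of seven named secondary outcomes are self-reports open to expectation, and the effort-dependent tests, including the primary one, are open to it to a lesser degree. The size of any such effect is unknown; the 7% to 26% range depends entirely on assumed shifts of 0.1 to 0.3 SD. The primary analysis, the sample size and the set of outcomes in the consistency reasoning need no change.

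The conclusion assumes that participants recognise the content of the sessions they attend. It does not assume that they know which program is experimental.

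**What to change.** In A1.1, replace the blinding sentence with: *Outcome assessors are blinded to allocation; treating therapists are not; participants know the content of their program.* If participants are in fact kept unaware of which program is experimental, add that and say how it is done. If not, leave it out.

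In A1.6, under Secondary Analyses, add: *WOMAC and VR-12, and to a lesser degree the effort-dependent performance and strength tests including the 6-minute walk, are open to expectation effects. Agreement among these outcomes will not be described as double-blind corroboration.*

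The cost is a few lines of text. The downside is a less favourable blinding claim in the protocol and in later reports.
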